4.11. Data quality assurance

The questionnaire will be pretested on 5% of the study population who will not participate in the main study in two study areas. Training on the verification and orientation of the study, the data collection tools, and the data collection process will be provided to data collectors a week prior to the start of data collection

During data collection, regular supervision and follow-up will be undertaken; the principal investigator (PI) will follow the collection process and will collect the filled questionnaire daily. The completeness and consistency of the daily data of individual participants will be checked. Missing data will be crosschecked and corrected before entered into a computer for analysis. The daily collected data was inserted into the locked patient data file on the computer accessed only by the PI

4.12. Data Processing and Analysis Procedure

After every data collection night, inconsistencies in data collection will be examined and fixed. Epi. Info version 7.2 will used for data entry and Statistical Package for the Social Sciences (SPSS) version 27will be used for data analysis.

The normality of data distributions for quantitative variables will be assessed using the Kolmogorov-Smirnov test and Levene's test will be used to check the homogeneity of variance. The plot of the Box will be used to check outliers. Histograms and visual inspection of individual data will be used to verify the data distribution.

Independent t-tests and ANOVA tests will be used to assess continuous data on pain severity at different postoperative times, and results will be presented as mean plus standard deviation. The categorical data of PONV at different postoperative times will be analyzed by chi-square or Fisher exact test and presented as frequencies, percentages, and a bar chart graphically. P-values of less than 0.05 will be determined as statistically significant.

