4.2. Study design

A multi-centered, randomized, controlled, single-blinded trial will be conducted at Dilla University General and Teaching Hospital and Hawassa University Comprehensive and Specialized Hospital.

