4.5. Sampling procedure and sample size

The sample size (N) was calculated by the formula for a continuous outcome variable with equal sample sizes in both groups, $n = 2[(Z_{\alpha}/2 + Z(1-\beta))^2 * \sigma^2]/(d^2)$ by G-power calculator. We assumed: significance level ($Z_{\alpha}/2$) = 0.05, taken 1.96, and power of study $Z(1-\beta)$ = 0.80, taken 0.84; σ^2 is the standard deviation taken from a previous study in South Korea⁴⁸, which is 1.9. Assuming a medium effect size in the OFA group compared to those receiving fentanyl is clinically significant, the calculated sample size for each group is 31, resulting in 62 participants in both groups. To account for potential contingencies, an additional 10% is added to the final sample size, resulting in 70 participants.

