4.6. Random sequence generation

The eligible participants presenting for gynecologic surgery at both study areas during the study period will be selected. Participants will be allocated to study groups by a computer-generated random allocation sequence number created by an independent anesthetist with a 1:1 allocation to the treatment group (T) and control group (C) the night before surgery.

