4.8.2. Independent variables

- Age
- Height
- Weight
- ASA physical status
- BMI
- Educational background
- Marital status
- Anesthetic experience
- Type of diagnosis and procedure
- Participants' hemoglobin and hematocrit
- Preoperative hemodynamic variables

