4.10. Data collection procedures

After getting ethical clearance from the Dilla University College of Health Sciences and Medicine ethical review board, a structured questionnaire will be formed and translated into the respective languages by the principal investigator (PI). Two BSC anesthetists involved in patient management will be selected at both study areas and trained in the overall process of participant handling and data collection.

During the preoperative period

Patients undergoing gynecologic operations during the study period will be assessed and told about the study process and anesthetic the day before the surgery. The patient will receive maintenance fluid, had bilateral peripheral IV lines secured, and was NPO the night before surgery. On the morning of the procedure, both a standard informed consent form for the procedure and a separate consent form for the study will be checked and available.

The availability and functionality of the bilateral IV line, and NPO status will be checked, and prophylactic drugs will be given. Standard preoperative questionnaires will be used, and data will be collected through patient responses and medical records, such as patient monitoring and charts.

At intraoperative period

Routine ASA monitoring will be checked and applied for patients in both groups when the patient presented to the OR. The functionality and availability of the bilateral IV line and urinary catheter will be rechecked. Propofol (3 mg/kg) will be given to induce anesthesia after the patient had been pre-oxygenated for both groups. An intravenous bolus of 0.5 mg/kg of ketamine during the induction phase for patients in the treatment group, then a continuous infusion of 0.2 mg/kg/hr. Of ketamine. A bolus of 1.5 mg/kg will be given before induction, and the same dose of lidocaine will be administered every 15 to 20 minutes after induction of anesthesia until the start of skin closure.

Patients in the control group will be induced with fentanyl 2 μ g/kg given during induction of anesthesia with propofol 3mg/kg. 0.5 μ g /kg of fentanyl will be given every 20-30 minutes up to the start of skin closure.

Intubation will be performed after administering 1.5–2 mg/kg IV suxamethonium. Inhalational anesthetics as availabilities (Isoflurane 0.75–2% and Halothane 1%_ 2%) were opened after the position of the ETT was confirmed, and Dexamethasone 0.15mg/kg IV bolus will be given after securing the ETT.

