Anesthesia will be maintained with inhalational agents according to the patient's tidal volume of 6–8 ml/kg adjusted to maintain oxygen saturation >95% with 3- 4 ml 100% oxygen flow, and end-tidal CO₂ between 32 and 45 mmHg. Muscle relaxation will be maintained with vecuronium 0.8 mg/kg. Intraoperative anesthesia depth will be assessed by clinical signs as well as by patient monitoring. Estimated intraoperative blood loss will be supplied with ringer lactate or normal saline.

The intraoperative participants' data will be collected from the anesthesia record chart and patient monitoring. Intraoperative hemodynamic variables will be collected every 10 minutes. Intraoperative cardiac adverse events such as intraoperative bradycardia (pulse rate less than 50 bpm), tachycardia (PR greater than 100 bpm), hypertension, and hypotension we diagnosed and managed as per institutional protocol. Intraoperative nausea or vomiting in both groups will also be managed as an institutional protocol.

When the surgeon begins skin closure, the inhalational agent will be turned off. A pre-prepared reversal agent bolus (neostigmine 0.05 mg/kg with atropine 0.02 mg/kg IV) was administered for patients given long-acting muscle relaxants after checking the adequacy of spontaneous ventilation, adequate movement of the respiratory bag, oxygen saturation >95percentage and ETCO₂ between 32 and 45 mmHg after the skin is closed.

During the postoperative period

The postoperative pain severity will be assessed by the validated VAS starting from the patient's discharge from PACU to 24 hours postoperatively. Data will be collected at discharge from PACU, at 6 hours, 12 hours, and 24 hours postoperatively. Analgesia request at postoperative times will be recorded as the patient's request for analgesia according to the VAS score. PONV data will be collected from the time of arrival at PACU at 6 hours, 12 hours, and 24 hours postoperatively according to the patient's signs and symptoms.

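### Section 4.12 states no hospital term for the VAS comparison in a two-hospital trial; adding one is a minor, optional improvement worth about 1 to 2 power points if the hospitals differ by 1 cm

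*Combined protocol and SAP*

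**What the plan says.** Section 4.2 sets out a two-hospital trial: "A multi-centered, randomized, controlled, single-blinded trial will be conducted at Dilla University General and Teaching Hospital and Hawassa University" (the sentence goes on to complete the second hospital's name). For the primary outcome, VAS pain at PACU discharge and at 6, 12 and 24 hours, Section 4.12 states that "Independent t-tests and ANOVA tests will be used to assess continuous data on pain severity at different postoperative times". It does not say which factors the ANOVA contains.

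Section 4.8.2 lists eleven independent variables, ending with "Preoperative hemodynamic variables". Hospital is not one of them.

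On randomization, Section 4.6 says "Participants will be allocated to study groups by a computer-generated random allocation sequence number created by an independent anesthetist with a 1:1 allocation". It neither states nor excludes stratification by hospital.

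The documents report no between-hospital difference in pain and no expected split of patients between the hospitals.

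**The concern.** If mean pain differs between the hospitals, that difference sits in the residual variance of an unadjusted t-test and costs some precision. If allocation is balanced within each hospital, the unadjusted test also ignores a feature of the design and becomes conservative. Precision and a slightly low rejection rate are all that is at stake. Randomization protects the treatment comparison from bias under either list structure.

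The documents leave some room for a hospital difference. Section 4.10 says "Two BSC anesthetists involved in patient management will be selected at both study areas" and has them trained in data collection, which could mean local raters. On postoperative analgesia it says "Analgesia request at postoperative times will be recorded as" the patient's request according to the VAS score, and names no common postoperative analgesic. Neither point shows that pain scores differ by hospital.

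**Working it through.** **Reproducing the plan's figure.** Section 4.5 gives 1.96 and 0.84, SD 1.9, 31 per group and 70 in total. The effect is given only in words: "Assuming a medium effect size in the OFA group compared to those receiving fentanyl is clinically significant". If medium is taken as 0.5 SD (0.95 cm, an assumption), the printed formula gives 2 × 2.8² / 0.5² = 62.7, so 63 per group. Leaving out the factor 2 gives 2.8² / 0.5² = 31.4, close to the stated 31. Keeping the factor 2 and solving for the effect that 31 per group can detect gives √(2 × 2.8² × 1.9² / 31) = 1.35 cm (0.71 SD). That implied effect is used below because it is the one consistent with the stated size and power.

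**Assumptions.** 35 per arm; two-sided 5%; 1.9 is the within-hospital SD; hospital difference *s* of 0, 0.5 or 1 cm; share *p* of patients in one hospital from 50:50 (worst case, since *p*(1−*p*) is largest there) to 80:20. Neither *s* nor *p* is in the documents.

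**One list, unadjusted.** The SD becomes √(1.9² + *s*²*p*(1−*p*)). At *s* = 1 and 50:50 this is √(3.61 + 0.25) = 1.965. The standard error is 1.965 × √(2/35) = 0.470, and the noncentrality is 1.35 / 0.470 = 2.87 on 68 df: power 80.9%.

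**One list, adjusted.** The SD is 1.9 on 67 df, averaged over the hypergeometric distribution of hospital mix between arms: power 82.8%, whatever *s* is. With exact balance within hospital it would be 83.4%, so chance imbalance costs about 0.6 points.

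**Per-hospital lists.** The noncentral t with inflated SD does not apply to the unadjusted test here, because balance within hospital removes the hospital difference from the estimate but not from its estimated standard error. Both analyses were therefore simulated under per-hospital lists (300,000 trials per cell, effect 1.351 cm, hospitals of 34 and 36 for the near-equal split).

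| Lists | *s* (cm) | Split | Unadjusted | Adjusted | Gain (points) |
|---|---|---|---|---|---|
| One | 0 | either | 83.4% | 82.8% | −0.6 |
| One | 0.5 | 50:50 | 82.8% | 82.8% | +0.1 |
| One | 0.5 | 80:20 | 83.0% | 82.8% | −0.2 |
| One | 1 | 50:50 | 80.9% | 82.8% | +1.9 |
| One | 1 | 80:20 | 81.8% | 82.8% | +1.0 |
| Per hospital | 0.5 | near 50:50 | 83.0% | 83.4% | +0.4 |
| Per hospital | 0.5 | 80:20 | 83.1% | 83.4% | +0.3 |
| Per hospital | 1 | near 50:50 | 81.5% | 83.3% | +1.8 |
| Per hospital | 1 | 80:20 | 82.3% | 83.4% | +1.1 |

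Gains are taken before rounding. Simulating the one-list case gives 1.0 to 2.1 points at 1 cm. Under one list the term breaks even at a hospital difference of 0.47 cm (50:50) to 0.59 cm (80:20).

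**Type I error (simulated).** Unadjusted: about 5% under one list; under per-hospital lists 4.3% (50:50) to 4.5% (80:20) at 1 cm. Adjusted: about 5% throughout.

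**Other readings.** If the true effect is 0.95 cm, one-list power at 1 cm is 53.4% adjusted against 51.4% (50:50) or 52.3% (80:20) unadjusted, a gain of 1.1 to 2.1 points. If 1.9 is the total SD, the one-list gain at 1 cm and 50:50 is again about 2 points (simulated).

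**The case against.** The strongest objection is that nothing in the documents shows a hospital difference. Eligibility, weight-based intraoperative regimens and the VAS are common to both hospitals. Section 4.11 promises that training on the tools and "the data collection process will be provided to data collectors a week prior to the start of data collection", with regular supervision by the principal investigator. The local-rater route is weak: Section 4.7 says the treating anesthetist takes no part in other study processes, which sits awkwardly with Section 4.10, so who rates pain at each hospital is unsettled. Silence on a postoperative analgesic is not evidence that practice differs by hospital. All of this stands, and it is why the gain can only be conditional.

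It is also fair that hospital's absence from Section 4.8.2 proves little, since Section 4.12 puts none of those variables into a model, and that the unspecified ANOVA could carry a hospital factor. Under a single list, the term can lose a little power when the hospitals are nearly alike.

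What survives is that the plan states neither the term nor the list structure. The adjusted model holds its error rate near 5% under either structure, and naming it now avoids a choice between two analyses after the data are seen.

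**Conclusion.** The omission is real but minor. The current comparison is unbiased, with valid or slightly conservative type I error. Adding hospital gains about 1 to 2 power points if the hospitals differ by 1 cm, and about 0 to 0.4 points at 0.5 cm. These figures rest on an assumed hospital difference and split, a within-hospital SD of 1.9, and the back-solved 1.35 cm effect.

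Three stronger readings are not supported:

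- A reader might infer a gain of about 2.5 points at 1 cm. That figure is 83.4% (adjusted, per-hospital lists) minus 80.9% (unadjusted, one list). It arises only if both randomization and analysis are changed, and is not the effect of the hospital term.
- A reader might infer that the two-hospital result would be biased or its error rate inflated. Neither follows under either list structure.
- A reader might point to larger gains (3.0 to 5.0 points at 1.5 cm under one list). These need a hospital difference above the implied treatment effect, which nothing in the documents suggests.

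The point is also small beside Section 4.5: if medium means 0.5 SD, power with 35 per arm is only about 54%, and a hospital term does not repair that.

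**What to change.** In Section 4.12, compare VAS between arms at each planned time with a linear model containing treatment and hospital as fixed effects, in place of the unadjusted t-test. If a repeated-measures ANOVA is used, add hospital as a between-patient factor. In Section 4.6, add one sentence saying whether there is one allocation list or one per hospital; this is worth stating whichever analysis is kept.

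Per-hospital permuted-block lists are optional. They recover the roughly 0.6 points that chance imbalance costs the adjusted model, and should be used only with the hospital term, because without it the test becomes conservative.

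The cost is one model degree of freedom and a few words of text, with no extra patients or data beyond recording the hospital. If the hospitals are alike, power falls by about 0.6 points under one list and by less than 0.1 point with per-hospital lists.

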SBP	Systolic Blood Pressure
SNNPR	Southern Nations Nationalities and Peoples Region.

III. Executive Summary

Background: Long-term use of opioids has been linked to various side effects and decreased patient satisfaction after anesthesia. A combination of drugs with opioid was used for intraoperative analgesia. Multiple drugs, by avoiding opioids, was a new opinion suggested. Opioid-free anesthesia with a combination of drugs is a new idea to avoid opioid from postoperative analgesia.

Objective: To determine the effectiveness of low-dose ketamine and intravenous lidocaine versus fentanyl for postoperative pain in patients undergoing elective gynecologic surgery under general anesthesia at Dilla University Teaching Hospital and Hawassa University Comprehensive and Specialized Hospital from April 10 to October 10, 2023.

Methodology: A multicenter, randomized, controlled, single-blinded superiority trial will be conducted with 70 adult patients undergoing elective gynecologic surgery under general anesthesia. Randomization will be done by a computer-generated random allocation sequence in equal ratios to the treatment group ($T = 35$) and the control group ($C = 35$). The primary dependent variable is the pain severity measured by a visual analog scale postoperatively at discharge from the post-anesthesia care unit, 6th hour, 12th hour, and 24th hour, and the secondary outcomes are postoperative nausea and vomiting, postoperative analgesia request, and intraoperative cardiac adverse events. Student's t-test, analysis of variance, and chi-square test will be used for data analysis. A p-value of less than 0.05 was determined as statistically significant.

Work plan and budgeting: - study will be conducted from April 10, 2023, to October 10, 2023, with a cost of 41625 ETB.

1. Introduction

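### Four correlated pain scores per patient, no repeated-measures method named: section 4.12 does not commit to one valid 5% test of the primary hypothesis

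*Combined protocol and SAP*

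**What the plan says.** - **Measurements.** VAS is the primary outcome. Section 4.10 sets four assessments per patient: "Data will be collected at discharge from PACU, at 6 hours, 12 hours, and 24 hours postoperatively".
- **Analysis.** Section 4.12: "Independent t-tests and ANOVA tests will be used to assess continuous data on pain severity at different postoperative times". The Executive Summary adds no detail: "Student's t-test, analysis of variance, and chi-square test will be used for data analysis".
- **Checks.** For variance, section 4.12 says "Levene's test will be used to check the homogeneity of variance". The other checks are a normality test, box plots and histograms. Nothing is said about sphericity, covariance structure or a patient term.
- **Threshold.** "P-values of less than 0.05 will be determined as statistically significant", with no adjustment for testing at several times.
- **Hypothesis.** The Hypothesis Testing text before section 3 compares one mean pain severity in the fentanyl group with one in the opioid-free group. Neither mean carries a time index, and no section names a primary time point.
- **Unit in the sample size.** Section 4.5 uses a two-means formula with one value per patient, and plans 35 patients per arm.

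**The concern.** Four scores from one woman are correlated, and a test that ignores this has the wrong error term. With only two arms, a one-way ANOVA between arms at a single time is the same test as the t-test (F = t²). For the comparison of arms, ANOVA therefore adds something only if it spans the times. The hypothesis, with its single mean per group, also calls for an answer that spans them.

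At stake is the error rate of the primary superiority claim. A pooled ANOVA would understate the standard error of the overall group difference. It would also put between-patient variance into the error term for group-by-time, so a real difference in the course of pain could be missed. Separate tests avoid both faults but give four chances to claim success, with no rule for combining them. Because the wording allows either route, the choice could be made after the data are seen.

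**Working it through.** **Inputs from the documents.** Two arms of 35 (sections 4.5 and 4.6); four scores per patient (section 4.10); threshold 0.05 (section 4.12), two-sided with z = 1.96 in section 4.5 ("0.05, taken 1.96, and power of study").

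**Assumed, because the documents give no value.** Within-patient correlation ρ, constant over the four times, shown from 0.1 to 0.7. No true difference between arms.

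**The plan's own figure.** The step from 31 to 35 per arm reproduces: 31/0.9 = 34.4, rounded up to 35, so 70 in total. The 31 itself does not follow if a medium effect is read as 0.5 SD: 2 × (1.96 + 0.84)²/0.5² = 62.7, so 63 per arm. That is a separate matter and does not affect this point, since the rates below barely depend on n.

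**Reading A: scores pooled in an ordinary group × time ANOVA.** The residual has 280 − 8 = 272 degrees of freedom. With n per arm and score variance σ²:
- variance used for the group difference: 2σ²/(4n)
- true variance: (2/n) × σ²(1 + 3ρ)/4
- ratio, true to used: 1 + 3ρ

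So the reported SE is 1/√(1 + 3ρ) of the true one, and the false-positive rate is about 2 × [1 − Φ(1.96/√(1 + 3ρ))]. At ρ = 0.5, 1.96/√2.5 = 1.240, which gives 21.5%. Half of these errors favour the opioid-free arm, against a nominal 2.5%.

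The true error variance for group-by-time is only (1 − ρ)σ², while the pooled residual estimates about σ². Its rate is about P(χ²₃ > 7.815/(1 − ρ)).

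**Reading B: a t-test, or the identical one-way ANOVA, at each time.** Each test uses one score per patient and holds 5%. If any one of the four may count as success, independent tests would give 1 − 0.95⁴ = 18.5%. With common correlation ρ the rate is 1 − ∫[Φ((1.96 − √ρ·u)/√(1 − ρ)) − Φ((−1.96 − √ρ·u)/√(1 − ρ))]⁴ φ(u) du.

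| ρ | 1 + 3ρ | Reported/true SE | A: group test | A: favouring opioid-free | A: group × time | B: at least one of four |
|---|---|---|---|---|---|---|
| 0.1 | 1.3 | 0.88 | 8.6% | 4.3% | 3.4% | 18.4% |
| 0.3 | 1.9 | 0.73 | 15.5% | 7.8% | 1.1% | 17.4% |
| 0.5 | 2.5 | 0.63 | 21.5% | 10.8% | 0.1% | 15.6% |
| 0.7 | 3.1 | 0.57 | 26.6% | 13.3% | <0.01% | 13.0% |

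**Check by simulation** (40,000 null trials per setting, 35 per arm, ρ = 0.1, 0.3, 0.5, 0.7):
- A, group test: 8.5%, 15.6%, 21.2%, 26.6%
- A, group × time: 3.2%, 1.1%, 0.2%, 0.0%
- B, at least one of four: 18.7%, 17.6%, 15.4%, 13.1%

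If correlation decays with distance in time (AR(1) at 0.3, 0.5, 0.7), the pooled group test rejects in 11.7%, 17.2% and 23.1% of trials.

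**Patient as the unit.** A t-test on patient means, which is the between-group test of a repeated-measures ANOVA, rejects in 4.9% to 5.2% of simulated trials at every correlation tried, with 31 or 35 per arm.

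**The case against.** A reader might infer that the planned ANOVA does treat the four scores as independent, so that the trial's false-positive rate is 15% to 27%. The documents do not support that.

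- The word independent qualifies the t-tests, not the ANOVA. No section pools 280 scores or defines an overall group test. A repeated-measures ANOVA is also an ANOVA.
- The next sentence of section 4.12 uses the same phrase about postoperative times for nausea and vomiting, with chi-square or Fisher tests. That suggests one comparison per time, and presenting means with standard deviations fits a per-time table.
- ANOVA could be meant for something else. Section 4.8.2 lists variables that may have more than two categories, such as educational background and type of procedure.
- Levene's test is a routine check for independent t-tests, so it is not evidence of pooling.
- The correlation is assumed, and the rate moves a good deal with it.

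All of this stands, and it makes the pooled figure conditional. It does not clear the plan. The per-time reading, at least as natural, leaves four unadjusted tests of a hypothesis that has no time index. Only a repeated-measures reading would give a valid overall group test from the named methods, and the plan does not commit to it.

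**Conclusion.** The concern holds in conditional form. The plan takes four correlated scores per patient, poses one comparison of means, and names tests without saying how they yield a single answer.

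- **If pooled as independent:** the overall group test rejects falsely about 15% to 27% of the time for ρ from 0.3 to 0.7 (about 9% at 0.1), and the group-by-time test falls to about 1% or below over the same 0.3 to 0.7.
- **If run separately at each time:** each test holds 5%, but the chance of at least one false positive is about 13% to 17% for ρ from 0.3 to 0.7, assuming that any one significant time could be claimed as success.

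These figures assume no true difference, equal correlation between times and complete data. They describe what the wording permits, not what the investigators have said they will do. This goes beyond missing detail, because neither plain reading tests the stated hypothesis at 5%, and a method that does is readily available.

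**What to change.** In section 4.12, replace the ANOVA on pain scores with one linear mixed model: patient as subject, unstructured covariance over the four times, and fixed effects for group, time and group × time. Name the time-averaged group difference from that model as the single primary test at two-sided 0.05. Naming the contrast matters, because once group × time is in the model the group difference could otherwise mean several things. Report per-time differences with confidence intervals as secondary, and bring the Executive Summary into line.

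A simpler form is one t-test on each patient's mean of the four VAS scores. With complete data it tests the same contrast. If some scores are missing, the mixed model is preferable, because patient means would then average over different times.

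**Cost.** Wording and minor analysis work; no added patients or data. The real consequence is that the primary estimand becomes the average over the four times, which the protocol has not yet stated, so the investigators should confirm that this is the comparison they intend before the data are analysed.

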4.8.1.2. Secondary outcome variables

- Postoperative analgesic requests between groups
- The occurrence of postoperative nausea and vomiting (PONV) between the groups
- The occurrence of intraoperative cardiac adverse events between groups

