4.9. Operational definitions

Nausea: The experience associated with the pressure to vomit

Opioid-free analgesia: A combination of various opioid-sparing techniques with absolute avoidance of opioids for pain relief in the pre-and postoperative periods.

Opioid-free anesthesia: It is a combination of various opioid-sparing techniques with absolute avoidance of opioids from induction of anesthesia until the extubation time

Postoperative nausea and vomiting: Any nausea, retching, or vomiting occurring in the first 24 hours after surgery

The Postoperative pain: pain felt up to 24 hours after an operation by the patient's expression

NRS: Valid and reliable tool for assessing pain intensity in all populations, regardless of literacy level([1](#), [50](#)). It employs a 0-to-10 rating scale, with zero representing no pain and 10 representing the worst possible pain.

VAS: This is a pain rating scale; the scores are derived from patient-reported valuations of symptoms that are recorded at 1 point along a 10 cm line that shows a continuum between the 2 edges of the scale, which are "no pain" and "worst pain([51](#))

Vomiting: Projection of contents of the stomach out through the mouth.

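### PONV is defined as one 24-hour yes/no outcome, but the only stated analysis tests it at separate times, with no stated 24-hour comparison, key time or multiplicity rule

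*Combined protocol and SAP*

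**What the plan says.** Section 4.9 (Operational definitions) defines postoperative nausea and vomiting as "Any nausea, retching, or vomiting occurring in the first 24 hours after surgery". That is one binary result per patient. Section 4.8.1.2 lists as a secondary outcome "The occurrence of postoperative nausea and vomiting (PONV) between the groups", and section 3.2 has a matching objective; neither names a time.

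Section 4.10 (postoperative period) says "PONV data will be collected from the time of arrival at PACU at 6 hours, 12 hours, and 24 hours postoperatively". The sentence clearly lists three looks. PACU arrival may be a fourth look or only the start of observation. It does not say whether a record describes the patient at that moment, since the last look, or since arrival.

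Section 4.12 contains the only sentence on PONV analysis: "The categorical data of PONV at different postoperative times will be analyzed by chi-square or Fisher exact test". It gives no rule for choosing between the two tests. The threshold is general: "P-values of less than 0.05 will be determined as statistically significant". The plan names no cumulative comparison, repeated-measures model, key time or multiplicity adjustment for PONV.

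**The concern.** The outcome is a single 24-hour incidence, while the stated analysis is a set of tests at separate times. Two consequences follow.

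First, nothing fixes in advance which comparison answers the PONV objective. With three or four tests at 0.05, the report could rest on whichever time is significant.

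Second, unless the 24-hour record is cumulative, each test sees only part of a patient's 24 hours. It then has fewer events and less power than a test of the defined outcome.

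Less PONV is one of the benefits that the protocol expects from avoiding opioids (section 1.2), so this secondary conclusion will be read with interest.

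**Working it through.** **Plan's own figure.** There is none to reproduce. The sample size in section 4.5 is for pain; no event rate or power is stated for PONV.

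**Inputs.**
- 35 per arm (executive summary).
- Threshold 0.05 (section 4.12).
- Three or four looks (section 4.10).
- Illustrative 24-hour rates from section 2.2: 15% (opioid-free) vs 31.7% (opioid) in a thoracoscopic lung resection trial. The same section reports 70.5% vs 71.4% in a gynaecological trial, that is, no difference.
- Assumption: Fisher's test replaces chi-square when an expected count is below 5. The plan does not state its rule.

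**Step 1. False positives, independent tests of true size 0.05.** The chance of at least one is 1 − 0.95^k.
- k = 3: 1 − 0.95³ = 0.143.
- k = 4: 1 − 0.95⁴ = 0.185.

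**Step 2. Effect of low event rates.** Exact binomial enumeration at 35 per arm, same true rate in both arms, four independent tests, 1 − (1 − size)⁴:

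| Per-time rate | Size, Fisher | Four tests, Fisher | Four tests, Fisher if expected count < 5, otherwise chi-square |
|---|---|---|---|
| 4.0% | 0.001 | 0.5% | 0.5% |
| 6.5% | about 0.005 | 2.2% | about 2.4% |
| 9.1% | 0.011 | 4.4% | 5.9% |
| 15% | 0.022 | 8.4% | 14.5% |
| 30% | 0.028 | 10.7% | 18.7% |

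Under this rule, about 14–19% for four tests arises only when per-time rates are roughly 15% or more. Uncorrected chi-square used throughout can slightly exceed 0.05 per test, so four tests can reach about 21%.

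**Step 3. Effect of within-patient correlation.** Simulation used 10,000 trials per scenario, latent correlation 0 to 0.9, and the same 24-hour rate in both arms (31.7% or 71.4%). The chance of at least one p < 0.05 was:
- chi-square throughout: 0.10–0.16 (three times), 0.13–0.21 (four times);
- switching to Fisher at low expected counts: 0.06–0.19;
- Fisher throughout: 0.04–0.12.

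One cumulative test gave 0.046–0.054 (Fisher 0.025–0.030).

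**Step 4. Power of one 24-hour test.** For 15% vs 31.7% at 35 per arm, exact power is 0.374 with chi-square and 0.282 with Fisher. About 100 per arm would be needed for 80%.

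**Step 5. Power per window, events spread evenly and independently over four windows.** The per-window rate is 1 − (1 − p)^(1/4).
- Opioid arm: 1 − 0.683^(1/4) = 0.091.
- Opioid-free arm: 1 − 0.85^(1/4) = 0.040.
- Expected events per arm under no difference: 35 × (0.091 + 0.040)/2 ≈ 2.3, so Fisher's test would usually apply.
- Exact power per window: 0.133 (chi-square), 0.028 (Fisher), 0.030 (switching rule).

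When correlation or three looks are allowed for, simulated power per time under the switching rule was 0.03–0.29, against 0.36–0.38 for the cumulative test.

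**The case against.** **A 24-hour test may be intended.** The outcome is stated as occurrence between groups, and section 4.10 can be read as recording from PACU arrival up to each time. If records are cumulative, the 24-hour test is the defined outcome and loses no power. This stands. A reader might infer that the 24-hour outcome will never be analysed, but the documents are only silent: they neither name such a test nor rule it out. What remains is that it is not prespecified among the three or four tests.

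**The two worst figures do not go together.** A reader might combine a 19% false-positive chance with 3% power per test. The 3% belongs to per-window rates of 4–9% with Fisher's test, where four independent tests give about 0.5–6% family-wise. The 14–19% needs higher per-time rates, or chi-square throughout. This objection also stands.

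**The power illustration is selective.** The rates come from lung surgery, the even and independent spread is assumed, and the cited gynaecological trial saw no difference. That is fair, so the figures show direction and rough size only.

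**Several looks may detect more.** Without adjustment, the chance that at least one time is significant was 0.11–0.48 for 15% vs 31.7% under the switching rule, sometimes above the cumulative test. This comes from having several chances at 0.05; after Bonferroni it was 0.04–0.28. At 71.4% against an assumed 40%, Bonferroni with correlated times can match or slightly exceed the cumulative test, so the power loss is not universal.

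**PONV is secondary, and one 24-hour test is itself weak.** Both are true. They limit how much this matters, but do not explain why the stated analysis differs from the stated outcome.

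**Conclusion.** The mismatch is plain in the text: a single 24-hour definition, per-time tests, no key time, no multiplicity rule and an undefined recording period. That part is certain.

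Its size depends on facts that the plan does not give. The family-wise false-positive chance is about 14% (three looks) or 19% (four) for independent tests of true size 0.05. It falls with correlation or Fisher's test, to about 0.5–6% for four independent tests at per-time rates of 4–9% with Fisher's test at low expected counts. Per-time tests are weaker than one 24-hour test in the illustration (3–13% against 37%), provided that the 24-hour record is not cumulative and events spread evenly and independently over four windows.

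The sponsor should correct this. It concerns one secondary outcome and does not touch the primary pain comparison.

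**What to change.** In section 4.12, name one PONV analysis: per-patient incidence of nausea, retching or vomiting at any point from PACU arrival to 24 hours. Test it once by chi-square or Fisher's test, with the rule for choosing stated, and report the risk difference with a 95% CI. Show the separate times descriptively, without p-values.

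In section 4.10 and on the data form, list the look times and state that each look covers the time since the last assessment, so that the 24-hour outcome can be built from the records.

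If the sponsor prefers to keep per-time tests as confirmatory, the plan should say so and adjust them; Bonferroni thresholds are 0.05/3 = 0.0167 or 0.05/4 = 0.0125.

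The cost of the main fix is a few sentences and possibly one reworded form item, with a note in data-collector training. No extra patients or visits are needed. Per-time p-values are given up. The change does not cure low power: at 35 per arm, the interval for the risk difference will be wide and should be read as such.
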